#### Control group:

The control group will receive the standard treatment + placebo for both types of intervention IMP at all times. If part or all the intervention therapy being investigated becomes standard treatment during the study, this may also be offered to the control group.

#### Intervention group:

The patients in the intervention group will also receive standard care. Immediately after randomisation to the intervention group, the patient will begin treatment with :

#### Azithromycin:

Day 1-3: 500 mg x 1

Day 4-15: 250 mg x 1

If the patient is unable to take the medication orally by themselves, the medication will, if possible, be administered by either stomach-probe, or alternatively, temporary be changed to clarithromycin 500 mg x 2 (this only in agreement with either study coordinator [name] or principal investigator [name]). This will also be done in the control group if necessary. The patient will switch back to azithromycin when possible.

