### **Hydroxychloroquine:**

Categorized as an anti-inflammatory and anti-malaria agent.

The drug is approved and marketed in Denmark for the prevention and treatment of malaria, for the treatment of rheumatoid arthritis, discoid and systemic lupus erythematosus and juvenile idiopathic arthritis.

Manufacturing, packaging and labelling of IMP:

The trial drugs (IMP) are manufactured by Glostrup pharmacy by pharmacist [name]. Placebo capsules are thus made similar to the intervention medicine. The drug (and Placebo) are labelled, according to Appendix 13. Glostrup pharmacy has a key for blinding. Therefore, it will always be possible to unblind a patient if indicated. Investigator must notify sponsor on grounds if a patient is unblinded.

Medical professionals dispense the IMP daily during hospitalization, except for patients preferring to handle their medication themselves. In the latter case, patient will fill in a medication diary (provided at randomisation). For all patients who are discharged during the intervention period, a medication diary will be provided. The medication diary is subsequently collected.

Exactly the amount of medication or placebo that the patient is required to take during the study periode will be provided, but for patients who do not take all the medication (protocol deviation), the remaining medication will be collected by the study staff. The patient will receive a follow-up phone call to check whether they have adhered to the medication schedule according to the trial protocol.

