## Proactive Prophylaxis With Azithromycin and Chloroquine in Hospitalised Patients With COVID-19 (ProPAC-COVID)

- Neurogenic hearing loss
- Psoriasis
- Retinopathy
- Maculopathy
- Visual field changes
- Breastfeeding
- Severe liver diseases other than amoebiasis (spontaneous INR > 1.5)
- Severe gastrointestinal, neurological and hematological disorders (investigator-assessed)
- eGFR <45 ml/min/1.73 m^2
- Clinically significant cardiac conduction disorders/arrhythmias or prolonged QTc interval (QTc (f) of > 480/470 ms).
- Myasthenia gravis
- Treatment with digoxin\*
- Glucose-6-phosphate dehydrogenase deficiency
- Porphyria
- Hypoglycaemia (Blood glucose at any time since hospitalization of <3.0 mmol/L)
- Severe mental illness which significantly impedes cooperation
- Severe linguistic problems that significantly hinder cooperation
- Treatment with ergot alkaloids

\*The patient must not be treated with digoxin for the duration of the intervention. For atrial fibrillation/flutter, select according to the Cardiovascular National Treatment Guide (NBV): Calcium antagonist, Beta blocker, direct current (DC) conversion or amiodarone. In case of urgent need for digoxin treatment (contraindication for the aforementioned equal alternatives), the test drug should be paused, and ECG should be recorded daily.

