### Drug Interactions

Interactions should be taken into account if the patient is taking other medications. For azithromycin, this includes antacids, ergotamine derivatives, colchicine and cyclosporine. For hydroxychloroquine, these include antidiabetic agents, tricyclic antidepressants, antipsychotics, halofantrine, cyclosporine, mefloquine, antiepileptic drugs, praziquantel and agalsidase.

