### 3.3.4 Intervention

Neither patients nor study staff will know which group the patient is allocated to. The medicine will be marked neutral, e.g. "Azithromycin group A" and "Azithromycin group B" and the same for Hydroxychloroquine.

NOTE: If the patient is receiving azithromycin prophylaxis, common practice is followed: the prophylaxis is paused and then restarted as usual.

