6. Respiratory medicine department, Odense University Hospital, Odense, Denmark. pi: [name], Research Associate Professor, Senior Consultant in Respiratory Medicine
7. Respiratory medicine department, Aarhus- and Aalborg University, PI: [name], Research Associate Professor, Senior Consultant in Respiratory Medicine

Patients will be randomized to one of the two treatment arms:

- i) **Intervention group:** Azithromycin day 1-3: 500 mg x 1, day 4-15: 250 mg x 1  
Hydroxychloroquine: Day 1-15: 200 mg x 2
- ii) **Control group:** The control group will always receive the standard treatment and placebo for both types of intervention medication. If part or all the intervention therapy being investigated becomes standard treatment during the study, this may also be offered to the control group.

The analyses described in this document will be performed by [name], PhD coordinating investigator, in cooperation with the sponsor and principal investigator [name], research associate professor, Respiratory Medicine Section, University of Gentofte Hospital, once the data have been entered, cleaned and released for use.

This document provides a detailed description of the statistical analyses that will be performed for the evaluation of the primary and secondary endpoints of protocolized for the ProPAC-COVID study.

The analyses described in this document are compatible with the recommendations of the CONSORT 2010 statement.

The International Conference on Harmonisation (ICH) of Good Clinical Practice (GCP)(1) and leading experts recommend that randomized clinical trials should be analyzed according to predefined outcomes and a predefined detailed statistical analysis plan (2). To prevent selective reporting of outcomes and data-driven analysis results and increase transparency this paper will in detail describe the detailed statistical analysis plan for the ProPAC-COVID trial while enrolment of patients and collection of data is still on-going and before the database is accessed for trial results.

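### On its most natural reading, the protocol lets a control who can take neither oral nor tube doses be changed to active clarithromycin, with no clinical indication and no described placebo

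*Protocol*

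**What the plan says.** Protocol section 3.3.4, under Azithromycin, covers the patient who cannot swallow the study drug. Tube dosing comes first. Failing that, treatment may "temporary be changed to clarithromycin 500 mg x 2", subject to agreement from the study coordinator or the principal investigator. The next sentence reads "This will also be done in the control group if necessary", and the paragraph closes by returning the patient to azithromycin when that becomes possible. The trigger is route of intake; no infection or other indication is required.

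Other parts of the plan bear on this:

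- Control treatment, protocol 3.3.4: "The control group will receive the standard treatment + placebo for both types of intervention IMP at all times".
- Control treatment, SAP Introduction: "The control group will always receive the standard treatment and placebo for both types of intervention medication".
- Blinding, protocol 3.3.4: "Neither patients nor study staff will know which group the patient is allocated to".
- Placebo supply, protocol paragraph on manufacturing, packaging and labelling: "Placebo capsules are thus made similar to the intervention medicine". No placebo for clarithromycin and no blinded clarithromycin supply is described anywhere.
- Interactions, protocol 3.3: "For azithromycin, this includes antacids, ergotamine derivatives, colchicine and cyclosporine". A second list covers hydroxychloroquine. Clarithromycin has none.

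**The concern.** A patient allocated to placebo who cannot take capsules or tube doses does not thereby need a macrolide. If the rule applies to controls as written, such a patient is given an active drug only to mirror what happens in the other arm. That contradicts the description of the control group in both documents. The one exception they state, trial therapy becoming standard treatment, does not cover this case.

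Two things are at stake. The main one is patient exposure: a control takes an unneeded drug that the allergy exclusion, the interaction lists and the side-effect lists do not name. The QTc stopping rule discontinues the trial product, without saying whether substituted clarithromycin counts as such. The lesser one is interpretation. The SAP counts QTc above 500 ms and ventricular arrhythmias by arm, so a macrolide-related event in a switched control would be counted in the placebo-arm rate.

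**Working it through.** **Step 1: which step extends to controls?** Two readings are possible.

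- *The clarithromycin switch, with or without the tube step.* The sentence on controls stands between the switch and the switch back, so the switch is its nearest antecedent. This reading conflicts with the two statements that controls receive placebo throughout.
- *The tube step only.* The switch would then be confined to active patients. Study staff do not know the arm, and nothing provides for unblinding the coordinator or principal investigator who must agree. As described, this could not be carried out blind.

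The first reading is the more natural one, and neither fits the rest of the protocol.

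**Step 2: how does the protocol handle similar situations?** If digoxin is urgently needed, "the test drug should be paused, and ECG should be recorded daily" (section 3.3, exclusion criteria footnote). If a macrolide is specifically needed and alternatives are lacking, azithromycin or its placebo may be stopped without unblinding (section 3.3.4, other antibiotics). Existing azithromycin prophylaxis is paused (section 3.3.4). The clarithromycin rule is the exception to this pattern.

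**Step 3: size.** The plan's own figure reproduces. With a difference of 1.5 days, SD 4, two-sided 5% and 80% power, the t-test needs 112.6, rounded up to 113 per arm, or 226 in total. This figure is not in dispute.

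The documents do not give the following inputs, so they are assumptions:

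- s, the share unable to take oral or tube doses, equal in both arms: 1% to 10%.
- f, the share of the contrast lost in those patients: 0.5.
- r, the excess QTc or arrhythmia risk from a macrolide: 5%, applied in full although the switch is temporary.
- Clarithromycin acts like azithromycin, for benefit and for harm.

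*Efficacy contrast.* Under the switch, active patients keep the effect and switched controls gain part of it: 1.5 − 1.5·s·f. Under a pause, active patients lose part of it and controls are unchanged: (1.5 − 1.5·s·f) − 0. The two are identical. At s = 5%: 1.5 − 1.5 × 0.05 × 0.5 = 1.4625 days.

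*Absolute harm difference.* Switch: r − s·r. Pause: r(1 − s) − 0. These are also identical; at s = r = 5%, both are 4.75 percentage points.

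*Placebo-arm excess.* Switch: s·r. Pause: 0. This is the only quantity of the three that differs.

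| s | Controls switched, of 113 | Contrast, switch or pause (days) | Placebo-arm excess under switch (points) | Expected extra placebo-arm events |
|---|---|---|---|---|
| 1% | 1.1 | 1.4925 | 0.05 | 0.06 |
| 5% | 5.7 | 1.4625 | 0.25 | 0.28 |
| 10% | 11.3 | 1.425 | 0.50 | 0.57 |

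**The case against.** **The reading is uncertain.** The paragraph sits under the intervention group and is written from that arm's side. A control cannot literally return to azithromycin, so drug names there may stand loosely for the blinded product. The pharmacy holds the key and could in principle supply a dummy. This stands as a reason for caution about intent. But no such supply is described, and if one was intended the text needs to say so.

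**The safeguards are real.** The switch is temporary, comes after tube dosing and needs agreement. Patients above 5 L/min oxygen, with prolonged QTc or on digoxin are excluded at entry. The treating physician may stop treatment at any time. The interaction section opens with a general duty to consider other medication, and its azithromycin list is not exhaustive. All of this stands, and it is why the point is minor.

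**The SAP partly captures the switch.** It tabulates azithromycin completion and antibiotic type, with a residual category that would take clarithromycin. The per-protocol analysis of the primary outcome, limited to those completing all intervention, would plausibly leave switched patients out. This also stands, so incomplete reporting is not the basis of the point.

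**Three stronger inferences are tempting and should not be drawn.**

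- *That the switch costs power which the fix restores.* Normal-approximation power at 113 per arm is 0.805 for 1.5 days and 0.785 for 1.4625 days. But on the assumptions above 1.4625 days also results from the pause.
- *That the fix makes the placebo arm macrolide-free.* Section 3.3.4 lets azithromycin prophylaxis restart, allows trial therapy for controls if it becomes standard, and allows a macrolide for specific need. The SAP lists azithromycin among non-study antibiotics.
- *That the placebo-arm rate moves by 0.9 points.* One event is 1/113 = 0.88 points, but only if it occurs. An expected shift of that size needs r of about 9% at s = 10%, or about 18% at s = 5%.

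**A pause is a trade-off.** It removes macrolide cover from active patients who cannot be dosed, and pre-emptive treatment of supra-infection is a stated aim. The loss is real but limited to a few days in few patients, and a macrolide stays available when clinically indicated.

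**Conclusion.** The point holds as a minor, cheaply corrected flaw. As most naturally read, the protocol permits an active macrolide in a control because of route of intake alone, with no clinical indication and no described placebo, against its own definition of the control group and that in the SAP.

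The consequence is unneeded exposure in probably very few patients: about 1 to 11 of 113 controls over an assumed 1% to 10%. With it comes an expected shift in the placebo-arm QTc and arrhythmia rate of about 0.25 percentage points at an assumed 5% switched and 5% excess risk.

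The equality of switch and pause for efficacy and for the harm difference depends on clarithromycin acting like azithromycin and on equal s and f under both rules; the documents establish none of these. The conclusion about exposure does not depend on them. It rests on the wording and on the absence of any described clarithromycin placebo.

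**What to change.** In protocol section 3.3.4, under Azithromycin, replace the clarithromycin option with: *If neither oral nor tube dosing is possible, azithromycin or azithromycin placebo is paused in both arms, without unblinding, and resumed when possible.* Clinically indicated macrolide use then stays under the existing rule on other antibiotics. Keep intention-to-treat as the main analysis; the sample size does not change.

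Optionally, add a row to the SAP's adherence data giving open-label macrolide use by arm, with dates.

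The cost is one protocol sentence and a few missed azithromycin days in the active arm. The optional row may also need a case report form field if dates are not already collected; the form is not among the documents, so this is unknown.

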#### Hydroxychloroquine:

Furthermore, the patient will be treated with hydroxychloroquine as follows:

Day 1-15: 200 mg x 2

## Proactive Prophylaxis With Azithromycin and Chloroquine in Hospitalised Patients With COVID-19 (ProPAC-COVID)

Follow-up is done on days 14, 29, 90 and 365 days, by accessing the electronic medical record system. The specific information obtained, and its purpose can be found in section 3.3.3.

### Regarding dosage

The Summary of Product Characteristics for Azithromycin suggests 500mg/day for three days or 500mg/day for one day and then 250mg daily for four days. However, other clinical studies have found a positive effect of a daily dose of 250 mg for prolonged periods as prophylactic treatment. Mortality among hospitalised patients with COVID-19 is quite high and the median time for hospitalisation is 10-15 days, so it seems reasonable to give patients prophylactic dose for 12 days.

The dosing of hydroxychloroquine follows the summary of product characteristics.

### Regarding other treatment with antibiotics:

If antibiotic therapy is deemed indicated to the patient due to e.g. pneumonia or if it becomes standard therapy, piperacillin-tazobactam should be given as an empirical treatment at a dose adjusted to renal function. In case of penicillin allergy, cefuroxime is also given at a dose appropriate to renal function, weight and age. When positive microbiology is available, immediately switch to targeted treatment.

If *specific suspicion of atypical pneumonia* is raised, ciprofloxacin is administered at a dose of corresponding to kidney function and concomitant examination for atypical pneumonia will be performed. If negative, ciprofloxacin is discontinued. If positive, ciprofloxacin treatment is continued for the duration of treatment corresponding to the microorganism detected. If there is a specific need for treatment with macrolide and where other options are not available (e.g. allergy to fluoroquinolones, or when there is an estimated need for combination treatment of e.g. legionella pneumonia), consult with an investigator, and in this case it may be decided to discontinue azithromycin (active) or azithromycin placebo. In this case, treatment stops without unblinding.

Furthermore, ECG recordings during the treatment period will be analysed with focus on QTc. At QTc (F) > 480/470 ms for respectively women and men, IMP will be discontinued for safety reasons (but the patient remains in the study).

### 3.3.5. Statistical analyses:

#### Primary endpoint:

- Number of days alive and discharged from hospital within 14 days (summarises both whether the patient is alive and discharged from hospital) ("Days alive and out of hospital")

#### Secondary endpoints:

## Proactive Prophylaxis With Azithromycin and Chloroquine in Hospitalised Patients With COVID-19 (ProPAC-COVID)

Secondary endpoint no. 1:

Ordinate outcome. The patient is categorized into one of the following 8 categories on day 15:

1. Dead
2. Hospitalised and mechanical ventilation or ExtraCorporalMembraneOxygenation (ECMO)
3. Hospitalised and Non-invasive ventilation or high-flow oxygen device
4. Hospitalised and given oxygen supplements that do not live up to oxygen supplements in (2) or (3) - e.g. oxygen on nasal catheter
5. Hospitalised and do not receive oxygen supplementation but need treatment (COVID-19 related or other)
6. Hospitalised and do not receive oxygen supplements and do not need treatment (just observed)
7. Discharged with restriction on activities, may be free of oxygen depletion or use LTOT ("home oxygen")
8. Discharged, no restrictions on activities

Other secondary endpoints:

- Admitted to the intensive care unit in the two groups (0 vs. 1) during the index admission
  - o For patients admitted to intensive care unit: number of days on intensive care (Length of stay, ICU)
- Have been on Non-Invasive Ventilation (NIV) (0 vs. 1) during index hospitalisation
- Dead at day 30
- Duration (days) of index hospital admission
- Days alive and discharged from hospital within 30 days (summarises both whether the patient is alive and discharged from hospital)
- Dead at day 90 (reported later)
- Dead within 12 months (reported later)
- Number of readmissions for all causes within 30 days
- Number of days on NIV or mechanical ventilation during index admission
- Delta PaO2 day 1 (baseline) to day 4 (72 hours). At the same time oxygen supplements and oxygen systems are registered
- Delta PaCO2 day 1 (baseline) to day 4 (72 hours)
- pH day 4 (72 hours)

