### 1.2 Aims:

The aim of this randomised GCP-controlled trial is to clarify whether combination therapy with macrolide azithromycin and hydroxychloroquine via anti-inflammation/immune modulation, antiviral efficacy and pre-emptive treatment of supra-infections can shorten hospitalisation duration (measured as "days alive and out of hospital" as the primary outcome), reduce the risk of non-invasive ventilation, treatment in the intensive care unit and death.

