#### *Lack of specific treatment*

## Proactive Prophylaxis With Azithromycin and Chloroquine in Hospitalised Patients With COVID-19 (ProPAC-COVID)

Despite the rapid spread of the disease globally, there is no solid data yet to recommend any specific treatments, and by that, symptomatic, organ supportive therapy is recommended, and in case of progression to severe acute respiratory failure mechanical ventilation (5). A high incidence of bacterial super-infections has been reported in patients with COVID-19 who died (50%) compared to survivors (1%) ( $p < 0.0001$ ), and likewise, an incidence of septic shock of 70% and 0%, respectively (2). Thus, there is an urgent need for treatments that can improve the course of the diseases in the individual patients, including positive impact on risk for hospital admission, duration of hospitalisation, risk of secondary infections and death.

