### Standard Treatment

As there is no specific treatment for COVID-19, standard assessment and treatment is based on organ supportive therapy such as oxygen therapy (central), fluid therapy, antibiotic therapy for secondary infections. If the disease progress to severe acute respiratory failure, the patients will often require referral to an intensive care unit for mechanical ventilation.

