## **Secondary objective and outcomes**

1. Categorization of hospitalization status [ Time Frame: 14 days]

The patient will be categorized into one of the following 8 categories depending on status of their hospitalization:

- a. Dead (yes/no)
- b. Hospitalized and receiving mechanical ventilation or Extra Corporal Membrane Oxygenation (ECMO) (yes/no)
- c. Hospitalized and receiving Non-invasive ventilation or "high-flow oxygen device" (yes/no)
- d. Hospitalized and given oxygen supplements different from (2) and (3) (yes/no)
- e. Hospitalized and without oxygen treatment, but receiving other treatment (both related to COVID-19 or other) (yes/no)
- f. Hospitalized for observation (yes/no)
- g. Discharged from hospital with restriction of activity level (yes/no)
- h. Discharged from hospital without any restrictions of activity level (yes/no)

For this analysis, the patient will be assigned a number between 1 and 8. Frequencies for the categories will be presented. Furthermore, the location on the scale for each group will be presented by median (IQR). Significance for differences will be calculated by a Wilcoxon-Sign-rank test (WSR).

Only one category can be "yes".

2. Admitted to intensive care unit, if admitted to ICU then length of stay [ Time Frame: 14 days]

Number of patients admitted to intensive care will be compared using chi-square test. Length of stay in ICU will be analyzed using a t-test. Days not alive within the time frame will be added to days at ICU. If days not alive are equal in the two treatment groups, we will further present days at ICU excluding days not alive.

3. Have used Non-invasive ventilation (NIV) during hospitalization [ Time Frame: 14 days]

Use of NIV will be compared by a chi-square test.

4. Mortality [Time Frame: 30 days ]

Differences in mortality will be displayed using the Kaplan-Meier plots method in combination with the log-rank test and as an adjusted analysis using Cox proportional hazards models, while adjusting for the following variables: Age (per year increase), sex (M/F), COPD GOLD C/D (Yes vs. No), Heart failure NYHA III-IV (Yes vs. no), Active smoker (Yes vs. No).

5. Length of hospitalization [ Time Frame: 14 days]

Length of hospitalization will be compared using t-test.

6. Days alive and discharged from hospital [ Time Frame: 30 days]

This is equal to the primary endpoint but with a longer time frame and will be analyzed like the that.

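### The NIV yes/no outcome gives patients who are intubated or die without NIV the same score as patients who never needed support

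*Protocol*

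**What the plan says.** Protocol 3.3.5, under the other secondary endpoints, scores "Have been on Non-Invasive Ventilation (NIV) (0 vs. 1) during index hospitalisation". SAP secondary outcome 3 sets a 14-day time frame for it and gives the whole analysis in one sentence: "Use of NIV will be compared by a chi-square test". Neither text mentions patients who are intubated or die without NIV.

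Protocol 1.2 gives the direction of benefit. The treatment is meant to "reduce the risk of non-invasive ventilation, treatment in the intensive care unit and death", so 0 is the favourable value.

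Secondary endpoint no. 1, in the same protocol section, ranks the states from worst to best. Category 1 is death, category 2 is mechanical ventilation or ECMO, and category 3 is "Hospitalised and Non-invasive ventilation or high-flow oxygen device".

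The SAP does deal with death for other outcomes. Outcome 2 adds days not alive to ICU days, and outcomes 9 (readmissions) and 10 (NIV days) name death as a competing risk. Outcome 3 has no such rule. The protocol also counts days on NIV and on mechanical ventilation together, whereas SAP outcome 10 counts NIV days only.

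**The concern.** Code 0 covers two opposite courses: patients who stayed well enough not to need ventilatory support, and patients who became too ill for NIV or died before receiving it. On the trial's own scale the second group did worse than the patients coded 1.

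Direct intubation is conceivable on the documents. Protocol 2.1 describes recommended care as supportive and, "in case of progression to severe acute respiratory failure mechanical ventilation". The Standard Treatment paragraph says that on such progression "the patients will often require referral to an intensive care unit for mechanical ventilation". Neither names NIV as a required earlier step.

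Reducing NIV is a stated aim. If active treatment moved patients past NIV to intubation or death, this outcome would report it as progress towards that aim. If active treatment prevented direct intubation, this outcome would give it no credit.

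**Working it through.** **Arm size.** The only design figure needed is the number per arm. Protocol 3.3.6 gives a difference of 1.5 days, SD 4, two-sided 5% and 80% power. The normal approximation is n = 2 × (1.960 + 0.842)² × 4² / 1.5² = 111.6, so 112 per arm. The exact t-test gives 112.6, so 113 per arm and 226 in total, as stated. No rate or power is given for NIV, so every rate below is an assumption.

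**One worked table.** Assume control has 23/113 with NIV (20.4%) and 11/113 ventilated or dead without NIV (9.7%). Suppose 12 would-be NIV patients in the active arm are instead intubated directly or die without NIV.

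- NIV as defined: 11/113 vs 23/113. Uncorrected chi-square = 226 × (23 × 102 − 90 × 11)² / (113 × 113 × 34 × 192) = 4.99, p = 0.026 in favour of active.
- Ventilation or death without NIV: 23/113 vs 11/113, p = 0.026 against active.
- NIV, ventilation or death: 34/113 vs 34/113, p = 1.00.

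At the same half shift, other control NIV rates give p = 0.12 (10%), 0.095 (15%) and 0.007 (30%). At a quarter shift, p is 0.23 to 0.47 across control rates of 10% to 30%.

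**How often the test would mislead.** The test is z = (p_C − p_A) / √[2p̄(1 − p̄)/113], significant if |z| > 1.96, with exact binomial probabilities summed over all possible tables. Assume control has 12% NIV and 8% ventilated or dead without NIV.

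| Shift out of NIV in active | NIV, control vs active | Ventilation/death without NIV | Combined | NIV test favours active | Combined test favours active |
|---|---|---|---|---|---|
| One quarter | 12% vs 9% | 8% vs 11% | 20% vs 20% | 11% | 2.5% |
| One half | 12% vs 6% | 8% vs 14% | 20% vs 20% | 36% | 2.5% |
| Two thirds | 12% vs 4% | 8% vs 16% | 20% vs 20% | 63% | 2.5% |

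**Two further assumed cases**, to see what a combined outcome can and cannot do:

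- Overall harm: NIV 12% vs 5%, ventilation/death without NIV 8% vs 18%, combined 20% vs 23%. The NIV test favours active in 49% of trials and the combined test in 0.6%. The combined test shows harm in only 8%, whereas ventilation/death without NIV tested alone shows it in 63%.
- Benefit only on direct intubation or death: NIV 10% in both arms, ventilation/death without NIV 10% vs 4%, combined 20% vs 14%. The NIV test shows benefit in about 3%, the combined test in about 23%, and the separate component in about 44%.

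The combined outcome removes the false benefit but dilutes movement between its parts, so the components have to be shown with it.

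**The case against.** A reader might infer that nothing else in the plan would expose such a shift. The documents do not support that. ICU admission, 30-day mortality, the ordinal scale and the primary outcome are all prespecified, and the SAP's second table shows primary and secondary outcomes together. The Standard Treatment paragraph places mechanical ventilation in the ICU, so a directly intubated patient should normally appear there. This stands, and it limits the consequence. It is not full cover. No rule ties the NIV result to those outcomes. Once SAP outcome 10 leaves out mechanical ventilation, the SAP names that state only at one time point on the ordinal scale, so a patient intubated and extubated before then shows only indirectly.

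A reader might also infer that many patients will bypass NIV, or that treatment will push them to do so. The documents say neither. They give no bypass rate and no mechanism. The trial is double-blind and stratified by site, so local device preference should balance between arms. The distortion needs treatment itself to change the route. Patients who have NIV and are then intubated or die are still coded 1.

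Nor do the documents label code 0 a success. The item is worded as a record of use, and 0 is favourable only through the stated aim.

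Finally, the larger percentages come from large shifts. At a quarter shift the NIV test misleads in about 11% of trials, against 2.5% in that direction with no true difference. The dilution seen in the harm case is also a fair criticism of a combined outcome reported without its parts.

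**Conclusion.** The point holds as a gap in the definition of one secondary outcome. Code 0 mixes the best course with two courses that the protocol ranks below NIV, so fewer NIV patients cannot by itself be read as benefit. The direction of the error follows from the wording.

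Its size rests on assumptions: 113 per arm, a control NIV rate of 12%, and the share of NIV patients that treatment shifts to direct intubation or death. On those assumptions the false-benefit rate is about 11% at a quarter shift, 36% at a half and 63% at two thirds. The primary analysis is untouched, and other outcomes would partly show the problem. The change is still worth making, because it is cheap and the SAP already handles death in neighbouring outcomes.

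**What to change.** In protocol 3.3.5 and SAP outcome 3:

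1. Compare NIV, mechanical ventilation/ECMO or death (0 vs. 1) by the same chi-square test, or Fisher's exact test where the SAP already allows it.
2. State one window. The protocol uses the index hospitalisation and the SAP 14 days. These must be reconciled first, because the choice decides whether a death after discharge counts.
3. Beside it, report by arm with 95% confidence intervals (a) any NIV and (b) mechanical ventilation/ECMO or death without NIV. State that any NIV alone will not be interpreted as benefit.
4. Reconcile SAP outcome 10 with the protocol's days on NIV or mechanical ventilation.

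The cost is wording in two documents and no new visits, since ventilation days and mortality are already protocol outcomes. The sponsor should confirm that the case report form records NIV and mechanical ventilation separately. The change should be made before unblinding, after which the SAP allows further analysis only on reviewer or editor demand. The small downside is that the combined outcome is broader than NIV and can hide a shift between its parts, which is why item 3 is needed.
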